## 5.5 Criteria for Subject Withdrawal

### 5.5.1 Withdrawal from Study Treatment

A subject must be withdrawn from study treatment if any of the following occurs:

- Subject withdrew consent
- Subject lost to follow-up
- Participation in another clinical study
- Any events that unacceptably endanger the safety of the subject
- Occurrence of an exclusion criterion which is clinically relevant and affects the subject's safety, if discontinuation is considered necessary by the Investigator and/or Sponsor
- Occurrence of AEs, for which discontinuation is desired or considered necessary by the Investigator and/or the subject (if applicable)
- Any DLT during the DLT observation period (applicable for Part I): Subjects experiencing DLTs as described in Section 6.2.4 will not receive further protocol therapy. Subjects who discontinue treatment must be followed on study until resolution of toxicity or until disease progression
- Disease progression: In case of disease progression per RECIST 1.1 ([Appendix III](#)), the subject should be withdrawn from study treatment. However, treatment may continue past the initial determination of disease progression per RECIST 1.1 ([Appendix III](#)) as long as the following criteria are met:
  - No new symptoms or worsening of previous symptoms (including laboratory values) indicating disease progression
  - Tolerance of treatment either as single agent **CCI**
  - Stable ECOG PS
  - Treatment beyond progression will not delay an imminent intervention to prevent serious complications of disease progression (for example, central nervous system metastases).
- The decision to continue treatment should be discussed with the Medical Monitor and documented in the study records.
- Subjects should be discontinued from treatment if there is further evidence of progressive disease (further progression is defined as an additional 10% increase in tumor burden volume from time of initial progressive disease) at the control  $\geq$  4 weeks and  $< 6$  weeks from the initial scan documenting disease progression; however, continued treatment is possible in consultation with the Medical Monitor. The assessment of clinical benefit should be balanced by clinical judgment as to whether the subject is clinically deteriorating and unlikely to receive any benefit from continued treatment. If the Investigator feels that the subject continues to achieve clinical benefit by continuing treatment, the subject should remain on the

study and continue to be monitored according to the Schedule of Assessments (Table 1, Table 2, and Table 3).

- If the administration of a prohibited concomitant medication (see Section 6.5.2) becomes necessary during the study, the subject will be withdrawn from study treatment (the Sponsor may be contacted to confirm whether study treatment must be discontinued prior to doing so)
- Occurrence of pregnancy
- Noncompliance that is deemed by the Investigator or the Sponsor to compromise subject safety or study integrity (see Section 6.9).
- Occurrence of any Grade  $\geq 3$  AEs and irAEs as defined in Section 6.2.4 or deemed necessary by Investigator or the Sponsor for subject safety.

All subjects who discontinue M4112 treatment **CCI** [REDACTED] should undergo the End of Treatment Visit (within 7 days), Safety Follow-up Visit (within  $30 \pm 3$  days), and a second Safety Follow-up Visit **CCI** [REDACTED] as indicated in the Schedule of Assessments (Table 1, Table 2, and Table 3) for full safety evaluation. Subjects who discontinue treatment must be followed on study until resolution of toxicity or until confirmed disease progression.

## 5.5.2 Withdrawal from the Study

Subjects may withdraw from the study at any time without giving a reason. Withdrawal of consent will be considered withdrawal from the study. In case of withdrawal, subjects will be asked to continue Safety Follow-up Visits.

A subject must be withdrawn from the study if any of the following occur during the study:

- Withdrawal of the subject's consent
- Participation in any other interventional study during the treatment duration of this study
- Subject lost to follow-up.

In case of withdrawal from the study, the assessments scheduled for the End of Treatment Visit should be performed (see Section 7.1.3), if possible, with focus on the most relevant assessments. In any case, the appropriate eCRF section must be completed.

If a subject fails to attend scheduled study assessments, the Investigator must determine the reasons and the circumstances as completely and accurately as possible.

Subjects who do not complete the DLT period for reasons other than a DLT/AE will not be replaced.

## 5.6 Premature Termination of the Study

The clinical study may be terminated prematurely or suspended at the request of Health Authorities or if new safety or efficacy information leads to an unfavorable benefit-risk assessment for any IMP. The Sponsor may discontinue the study if it becomes unjustifiable for

medical or ethical reasons, for poor enrollment, or because of discontinuation of clinical development of an IMP or withdrawal of an IMP or comparator from the market for safety reasons.

Health Authorities and Independent Ethics Committees (IECs)/Institutional Review Boards (IRBs) will be informed about the discontinuation of the study in accordance with applicable regulations. The study may be terminated or suspended upon request of the Health Authorities.

In the situation of a premature termination of the study, subjects on treatment who are having a clinical benefit may continue to receive the IMP based on the Investigator's request and in consultation and agreement with the Sponsor.

## 5.7                   **Definition of End of Study**

The end of study is defined as the last subject having completed the last Safety Follow-up Visit, and/or stopped due to unacceptable toxicity, disease progression, Investigator/subject decision, withdrawn consent, lost to follow-up or has died, whichever comes first.

## 6                           **Investigational Medicinal Product and Other Drugs Used in the Study**

The term "Investigational Medicinal Product" refers to an active substance or a placebo being tested or used as a reference therapy in a clinical study, including products that have a marketing authorization but are formulated, packaged, or administered differently from the authorized form, used for an unauthorized indication, or used to gain further information about the authorized form. In this study, the IMPs are M4112, CCI [REDACTED].

### 6.1                           **Description of Investigational Medicinal Products**

[figure not shown]
CCI

CCI

CCI

## 6.2 Dosage and Administration

Subjects will be administered an oral dose of M4112 BID (or a regimen determined by the SMC) at least 1 h prior to a meal and at least 2 h after a meal in 28-day cycles. The SMC may need to make changes on the dosing and regimen (eg, BID to QD) of M4112. Meal times should be collected on the appropriate eCRF.

### 6.2.1 Dose Escalation Cohort (Part I)

#### 6.2.1.1 Subjects Receiving M4112 as Single Agent

##### Administration of M4112:

BID continuous administration of M4112 as single agent at doses recommended by the SMC is foreseen. On study site visit days, the morning dose of M4112 will be taken at the study site.

CCI [REDACTED]

##### Administration of M4112:

BID continuous administration of M4112 as single agent at doses recommended by the SMC is foreseen. On infusion day visits, **M4112 will be administered after premedication (within 30 min)** CCI [REDACTED]

CCI [REDACTED]

CCI [REDACTED]

CCI [REDACTED]

CCI [REDACTED]

CCI [REDACTED]

CCI

- Subjects in Part I of the study who experience a Grade  $\geq 3$  nonhematological AEs (for exceptions see DLT criteria) or Grade 4 hematological ADR, **after completion** of the DLT assessment period (ie, first 28 days of treatment with M4112), need to interrupt study treatment; however, subjects may continue on study treatment of M4112 at a reduced dose provided the reaction has resolved to baseline value or Grade  $\leq 1$  within 2 weeks and there is no progressive disease. The dose of M4112 will be reduced to a dose defined by the SMC. If indicated, a further dose reduction is possible.

- At evidence of hepatocellular injury attributable to study drug, such as increase in AST or ALT  $\geq 5$ -fold ULN or  $\geq 3 \times$  ULN elevation of ALT or AST and elevation of serum total bilirubin to  $\geq 2 \times$  ULN, without initial findings of cholestasis (elevated serum alkaline

phosphatase) or other apparent clinical causality (eg, viral hepatitis A, -B, or -C, alcohol abuse or co-medication (ie, paracetamol [acetaminophen]), subjects should interrupt study treatment and undergo close observation. This should include monitoring for symptoms (clinical signs of hepatitis, or hypersensitivity, fatigue, decreased appetite, nausea, vomiting, abdominal pain, jaundice, fever, or rash) and hepatic function (AST, ALT, alkaline phosphatase [ALP]) and fractionated bilirubin) at least every 3 days, until symptoms and/or hepatic function abnormalities resolve, stabilize or return to baseline values. This event should be reported to the Sponsor within 24 h of learning of its occurrence. Re-exposure of the subject to the study drug and possible dose level reduction will be determined by the SMC.

- Once the dose of M4112 has been reduced in an individual subject, it must not be escalated again
- If more than 2 dose reductions of M4112 are indicated, the subject will be permanently discontinued from study treatment
- M4112 must also be permanently discontinued in case study treatment delays exceed 2 weeks, regardless of the reason for delay
- Subjects who experience an increase in QT: Subjects in which the calculated QTc average (using the Fridericia correction calculation) increases to  $> 500$  ms on any triplicate reading or  $\geq 60$  ms change over baseline during treatment with M4112 have to interrupt study treatment until further clinical evaluation.

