Grade 1 to 2 Covering ≤ 30% body surface area	Continue CCI [REDACTED] M4112 therapy Symptomatic therapy (for example, antihistamines, topical steroids)	If persists > 1 to 2 weeks or recurs: Withhold CCI [REDACTED] M4112 therapy Consider skin biopsy CCI [REDACTED] [REDACTED] If worsens: Treat as Grade 3 to 4
Grade 3 to 4 Covering > 30% body surface area; life threatening consequences	Withhold CCI [REDACTED] M4112 therapy for Grade 3. Permanently discontinue for Grade 4 or recurrent Grade 3 Consider skin biopsy Dermatology consult 1.0 to 2.0 mg/kg/day prednisone or equivalent	If improves to Grade 1: Taper steroids over at least 1 month and add prophylactic antibiotics for opportunistic infections CCI [REDACTED]

Pulmonary irAEs		
Grade of Pneumonitis (NCI-CTCAE 4.03)	Initial Management	Follow-up Management
Grade 1 Radiographic changes only	Consider withholding CCI [REDACTED], or M4112 therapy Monitor for symptoms every 2 to 3 days Consider Pulmonary and Infectious Disease consults	Re-assess at least every 3 weeks If worsens: Treat as Grade 2 or Grade 3 to 4
Grade 2 Mild to moderate new symptoms	Withhold CCI [REDACTED] M4112 therapy Pulmonary and Infectious Disease consults Monitor symptoms daily, consider hospitalization 1.0 to 2.0 mg/kg/day prednisone or equivalent Consider bronchoscopy, lung biopsy	Re-assess every 1 to 3 days If improves: When symptoms return to near Baseline, taper steroids over at least 1 month, consider prophylactic antibiotics for opportunistic infections, and then resume CCI [REDACTED] M4112 therapy following steroids taper If not improving after 2 weeks or worsening: Treat as Grade 3 to 4
Grade 3 to 4 Grade 3: Severe new symptoms;	Permanently discontinue CCI [REDACTED] M4112 therapy	If improves to Baseline: Taper steroids over at least 6 weeks

Pulmonary irAEs		
Grade of Pneumonitis (NCI-CTCAE 4.03)	Initial Management	Follow-up Management
New/worsening hypoxia; Grade 4: life-threatening	Hospitalize Pulmonary and Infectious Disease consults 1.0 to 2.0 mg/kg/day prednisone equivalent Add prophylactic antibiotics for opportunistic infections Consider bronchoscopy, lung biopsy	If not improving after 48 h or worsening: Add additional immunosuppression (for example, infliximab, cyclophosphamide, iv immunoglobulin, or mycophenolate mofetil)

Hepatic irAEs		
Grade of Liver Test Elevation (NCI-CTCAE 4.03)	Initial Management	Follow-up Management

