Grade 1 Grade 1 AST or ALT > ULN to 3.0 x ULN and/or total bilirubin > ULN to 1.5 x ULN	Continue CCI [REDACTED] [REDACTED] M4112 therapy	Continue liver function monitoring If worsens: Treat as Grade 2 or 3 to 4
Grade 2 AST or ALT > 3.0 to $\leq$ 5 x ULN and/or total bilirubin > 1.5 to $\leq$ 3 x ULN	Withhold CCI [REDACTED] [REDACTED] M4112 therapy Increase frequency of monitoring to every 1 to 2 days 1.0 to 2.0 mg/kg/day prednisone or equivalent. Add prophylactic antibiotics for opportunistic infections Consult gastroenterologist/ hepatologist Consider obtaining MRI/CT scan of liver and liver biopsy if clinically warranted	If returns to Baseline: Taper steroids over at least 1 month, consider prophylactic antibiotics for opportunistic infections, and resume CCI [REDACTED] M4112 therapy following steroids taper. If worsens: Treat as Grade 3-4.
Grade 3 to 4 AST or ALT > 5 x ULN and/or total bilirubin > 3 x ULN	Discontinue CCI [REDACTED] [REDACTED] M4112 therapy Increase frequency of monitoring to every 1 to 2 days 1.0 to 2.0 mg/kg/day methylprednisolone iv or iv equivalent Add prophylactic antibiotics for opportunistic infections Consult gastroenterologist Consider obtaining MRI/CT scan of liver and liver biopsy if clinically warranted (for	If returns to Grade 2: Taper steroids over at least 1 month If does not improve in > 3 to 5 days, worsens or rebounds: Add mycophenolate mofetil 1 gram (g) twice daily If no response within an additional 3 to 5 days, consider other immunosuppressants per local guidelines

Hepatic irAEs		
Grade of Liver Test Elevation (NCI-CTCAE 4.03)	Initial Management	Follow-up Management
	study sites in Germany, only MRI is to be used)	

Renal irAEs		
Grade of Creatinine Increased (NCI-CTCAE 4.03)	Initial Management	Follow-up Management
Grade 1 Creatinine increased > ULN to 1.5 x ULN	Continue CCI [REDACTED] M4112 therapy	Continue renal function monitoring If worsens: Treat as Grade 2 to 3 or 4
Grade 2 Creatinine increased > 1.5 to 6 x ULN	Withhold CCI [REDACTED] M4112 therapy Increase frequency of monitoring to every 3 days 1.0 to 2.0 mg/kg/day prednisone or equivalent. Add prophylactic antibiotics for opportunistic infections Consider renal biopsy	If returns to Baseline: Taper steroids over at least 1 month, and resume CCI [REDACTED] M4112 therapy following steroids taper. If worsens: Treat as Grade 4.

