Grade of other irAEs (NCI-CTCAE 4.03)	Grade of other irAEs (NCI-CTCAE 4.03)	Grade of other irAEs (NCI-CTCAE 4.03)
	Initial Management	Follow-up Management
Grade 2 or Grade 3 clinical signs or symptoms suggestive of a potential irAE	Withhold CCI [REDACTED] M4112 therapy pending clinical investigation	If irAE is ruled out, manage as appropriate according to the diagnosis and consider re-starting CCI [REDACTED] M4112 therapy If irAE is confirmed, treat as Grade 2 or 3 irAE
Grade 2 irAE or first occurrence of Grade 3 irAE	Withhold CCI [REDACTED] M4112 therapy 1.0 to 2.0 mg/kg/day prednisone or equivalent Add prophylactic antibiotics for opportunistic infections Specialty consult as appropriate	If improves to Grade 1: Taper steroids over at least 1 month and resume CCI [REDACTED] M4112 therapy following steroids taper
Recurrence of same Grade 3 irAEs	Permanently discontinue CCI [REDACTED] M4112 therapy 1.0 to 2.0 mg/kg/day prednisone or equivalent Add prophylactic antibiotics for opportunistic infections Specialty consult as appropriate	If improves to Grade 1: Taper steroids over at least 1 month
Grade 4	Permanently discontinue CCI [REDACTED] M4112 therapy 1.0 to 2.0 mg/kg/day prednisone or equivalent and/or other immunosuppressant as needed Add prophylactic antibiotics for opportunistic infections Specialty consult.	If improves to Grade 1: Taper steroids over at least 1 month
Requirement for 10 mg per day or greater prednisone or equivalent for more than 12 weeks for reasons other than hormonal replacement for adrenal insufficiency Persistent Grade 2 or 3 irAE lasting 12 weeks or longer	Permanently discontinue CCI [REDACTED] M4112 therapy Specialty consult	

ALT = alanine aminotransferase; AST = aspartate aminotransferase; CT = computed tomography; irAE = immune-related adverse event; MRI = magnetic resonance imaging; NCI-CTCAE 4.03 = National Cancer Institute-Common Terminology Criteria for Adverse Events Version 4.03; T4 = thyroxine; TSH = thyroid-stimulating hormone; ULN = upper limit of normal.

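### Four rows of Protocol Table 9 tell sites to restart M4112 after a steroid taper of at least 1 month, which the 2-week permanent-stop rule in Section 6.2.3 does not allow

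*Protocol*

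**What the plan says.** The treatment-modification rules are listed in the Protocol's table of contents as Section 6.2.3. The heading is hidden in the released text, but the bullets are visible. One of them is absolute: "M4112 must also be permanently discontinued in case study treatment delays exceed 2 weeks, regardless of the reason for delay".

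Section 6.5.5.3 says irAE treatment should follow Table 9, and the table's title covers M4112 as a single agent. Four rows withhold M4112 at first and then, on recovery, tell the site to restart it:

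- **Pulmonary, Grade 2:** "taper steroids over at least 1 month, consider prophylactic antibiotics for opportunistic infections, and then resume", ending "M4112 therapy following steroids taper".
- **Hepatic, Grade 2:** "If returns to Baseline: Taper steroids over at least 1 month, consider prophylactic antibiotics for opportunistic infections, and resume", with the same ending.
- **Renal, labelled Grade 2:** "Taper steroids over at least 1 month, and resume", with the same ending.
- **Other irAEs, Grade 2 or first Grade 3:** "Taper steroids over at least 1 month and resume", with the same ending.

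In each row a redaction sits between the verb and M4112, but M4112 is visibly among what is restarted.

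The renal row covers creatinine above 1.5 and up to 6 times ULN. The row above it sends worsening patients to Grade 2 to 3 or Grade 4 management, and this row sends worsening patients to Grade 4. It therefore reads as spanning Grades 2 and 3 despite its label.

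**The concern.** A site managing one of these events has two instructions that cannot both be followed. Section 6.2.3 ends M4112 for good once the hold passes 2 weeks. Table 9, which the physician treating the event will have open, says to restart after a taper that lasts longer than that. Nothing visible in Table 9 points back to Section 6.2.3, and the withdrawal list in Section 5.5.1 does not contain the 2-week rule.

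The first thing at stake is re-exposure. A patient who has recovered from a pulmonary, hepatic, renal or other irAE could be given a first-in-human drug again when a mandatory rule says it should already have been stopped.

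The second is the descriptive data. SAP Section 15.2 sorts adverse events by the action recorded for M4112, with separate codes for interruption and withdrawal, and Section 15.2.1 tabulates them. The same clinical course would be coded differently depending on which rule the site followed. Treatment duration (SAP Section 13) would differ too.

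**Working it through.** The plan gives no figure to reproduce. The check is whether any hold can satisfy both rules.

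**Inputs**

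- Limit on a hold, Section 6.2.3: 2 × 7 = 14 days.
- Steroid taper T, Table 9: at least 1 month. This is 28 days at the shortest, or 30.4375 days by the conversion in SAP Section 9.
- Time R from the start of the hold to the recovery that starts the taper: 0 days or more.
- Dosing: continuous, twice daily (Section 6.2.1.1).

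**Hold under the four rows:** H = R + T.

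With the most favourable value, R = 0:

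| Taper | Hold | Days over limit | Ratio to limit |
|---|---|---|---|
| 28 days | 28 | 28 − 14 = 14 | 28/14 = 2.0 |
| 30.4375 days | 30.4375 | 30.4375 − 14 = 16.4 | 30.4375/14 = 2.2 |

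In doses, at least 28 × 2 = 56 are missed, against 14 × 2 = 28 within the limit.

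Compliance needs R + T ≤ 14. With T ≥ 28 this requires R ≤ −14, which is impossible. The overlap is empty, and real recovery time only widens the gap. For pneumonitis the table contemplates a substantial R: "If not improving after 2 weeks or worsening: Treat as Grade 3 to 4". That trigger does not cap the hold, because a slowly improving patient may start the taper later and the taper has no maximum. Only the lower bound is supported.

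**Is a withheld drug a delayed one?** The visible text does not separate the two. With continuous twice-daily dosing, withholding M4112 delays study treatment.

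**Rows left out**

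- Grade 2 diarrhea/colitis restarts on improvement to Grade 1, with no taper.
- Grade 3 diarrhea/colitis names a restarted drug that is redacted.
- The rash rows have redacted follow-up text.
- The endocrine rows tie restart to symptoms, tests or MRI, not to a completed taper.

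**Effect on DLT evaluation.** A hold of 28 days or more that starts on or after Day 1 runs to at least the end of Cycle 1 (Day 28). No restart under these rows falls inside the DLT window, so Cycle 1 dosing is the same whichever rule governs a later restart. Grade 2 events are not DLTs under the Grade 3 threshold, and under Section 6.2.4 doses missed for safety reasons do not make a subject unevaluable. The word generally is still needed, because Section 6.2.4 lets the SMC take later-cycle events into account.

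**The case against.** **The stronger rule already wins.** Section 6.2.3 is phrased as an obligation that applies whatever the reason, while Section 6.5.5.3 introduces Table 9 as guidance. On ordinary reading the 2-week rule controls. This stands, and it is why the point is about an unreconciled instruction rather than a missing rule. It does not remove the problem: the four restart instructions then have no valid use, and Table 9 does not say so. The omission from Section 5.5.1 adds little, since the neighbouring stop after more than 2 dose reductions is not listed there either.

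**Other provisions already restrict some of these patients.** This stands in part. Grade 3 events in the renal and other-irAE rows are restricted by Section 5.5.1, Section 6.5.5, the first visible bullet of Section 6.2.3 and, in Cycle 1, Section 6.2.4. Hepatocellular injury attributable to study drug is referred to the SMC for re-exposure. Grade 2 events outside that liver definition are not covered.

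**Sponsor oversight.** Section 3.4.2.1 requires irAEs to be reported within 24 h, which lowers the risk that sites diverge. It does not tell anyone which text to apply weeks later.

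**Redaction.** A qualifier may be hidden before the Section 6.2.3 bullets or inside the four rows. It cannot be excluded, although a rule that disregards the reason for delay makes a hidden exception less likely.

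**Readings that go too far.** A reader might treat Table 9's final stop, which includes "Persistent Grade 2 or 3 irAE lasting 12 weeks or longer", as a rival 12-week hold limit and compare it with 14 days. That row times the irAE or the steroid requirement, not a drug hold, so the ratio means nothing. A reader might also infer that restarting after a month is shown to be unsafe, or that the count of withdrawn patients must change. Table 9 requires recovery and a completed taper before restart, nothing visible compares that with an earlier restart, and no irAE rate is given.

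**Conclusion.** The two rules are incompatible as written. In four rows of Table 9 the shortest possible hold is about 1 month (28 days or more), at least twice the 14-day limit, so no restart under those rows can comply with Section 6.2.3. The wording favours the 2-week rule, but the table does not defer to it.

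The consequence is possible re-exposure contrary to a mandatory stop, together with ambiguous interruption, withdrawal and treatment-duration data. DLT counts and the Bayesian model are not generally affected. The number of patients involved cannot be estimated.

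The conclusion rests on visible text only, on a month being at least 28 days, and on a withheld drug counting as a delayed one. Confidence is high for the clash of wording and does not extend to any clinical harm. It should be corrected as an internal inconsistency. Because SAP Sections 4 and 7 report early termination, the practical value is for any subject still on treatment, for data review before database lock, and for any reuse of this text.

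**What to change.** State in Section 6.5.5.3 and in Table 9 that the 14-day limit of Section 6.2.3 governs M4112. Remove the M4112 restart instruction from the four rows, or qualify it so that it cannot apply once a hold exceeds 14 days. Add a cross-reference in Section 5.5.1, and align the Grade 3 part of the renal and other-irAE rows with Sections 5.5.1 and 6.5.5.

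If the sponsor does intend re-exposure after longer irAE holds, it should instead write an explicit irAE exception, with a maximum hold, into Section 6.2.3. That is a clinical choice. Keeping the 14-day limit ends M4112 for patients who recover and complete the taper, in a population with few alternatives, though Section 6.2.3 already requires this.

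For the final analysis, holds over 14 days followed by a restart can be looked for in the exposure listing of SAP Section 13 and discussed at the data review meeting. The programmed deviation checks visible in SAP Section 18.1 include none for this.

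The cost is an amendment or clarification letter, with no added patients, visits or procedures.

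### On the visible text, the 2-week limit on M4112 delays cannot be followed together with four Table 9 rows that resume M4112 after a steroid taper of at least 1 month, and at least five Table 9 resume rows can cover a Cycle 1 DLT without saying so (minor, safety wording)

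*Protocol*

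**What the plan says.** **The limit on delays.** The visible treatment-modification bullets (the 6.2.3 heading itself is not visible in the public copy) include: "M4112 must also be permanently discontinued in case study treatment delays exceed 2 weeks, regardless of the reason for delay".

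**Table 9, section 6.5.5.3.** Four rows visibly name M4112 as the drug to withhold and later resume after the taper:

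- Pulmonary Grade 2: "When symptoms return to near Baseline, taper steroids over at least 1 month, consider prophylactic antibiotics for opportunistic infections, and then resume". The same cell sets the time allowed before escalation: "If not improving after 2 weeks or worsening: Treat as Grade 3 to 4".
- Hepatic Grade 2: "If returns to Baseline: Taper steroids over at least 1 month, consider prophylactic antibiotics for opportunistic infections, and resume".
- Renal Grade 2: "If returns to Baseline: Taper steroids over at least 1 month, and resume".
- Other irAEs, in the row labelled "Grade 2 irAE or first occurrence of Grade 3 irAE": "If improves to Grade 1: Taper steroids over at least 1 month and resume".

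**Stopping after a DLT.** Sections 5.5.1 and 6.2.4 bar further protocol therapy for a subject with a DLT in the DLT observation period. Section 6.2.4 counts as a DLT any nonhematological AE or irAE of Grade 3 or higher in Cycle 1, apart from listed exceptions. It also has a hepatic criterion: drug-attributed ALT or AST of at least 3 x ULN with total bilirubin of at least 2 x ULN, without cholestasis or another apparent cause. For the same liver picture, 6.2.3 leaves re-exposure to the SMC.

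**The concern.** Two sets of instructions for the same subject disagree. A site that follows Table 9 keeps M4112 on hold through the taper and restarts it. A site that follows 6.2.3 stops it for good after 2 weeks. The likely cost is withdrawal of a subject whom Table 9 would have resumed, or different handling across the approximately 3 to 5 sites.

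The second part runs the other way. An investigator working from Table 9 alone is told to resume, or consider re-starting, M4112 after events that end treatment if they occur in Cycle 1. For liver events the row also leaves out the SMC. Section 3.4.2.1 makes liver toxicity and irAEs AESIs in this first-in-human study, so these rows should be unambiguous.

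**Working it through.** No planned figure is at stake. The check compares durations, then sets each resume row against the DLT rules.

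**1. Limit against taper**

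- Limit (6.2.3): 2 x 7 = 14 days.
- Taper (Table 9): at least 1 month. The shortest calendar month is 28 days; the SAP conversion in Section 9 is 30.4375 days.
- Excess over the limit: 28 - 14 = 14.0 days, or 30.4375 - 14 = 16.4 days.
- Ratio: 28/14 = 2.0, or 30.4375/14 = 2.2.

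This counts only the taper; time on steroids before it adds to the hold. As an illustration, take a pulmonary Grade 2 subject who reaches near-baseline symptoms on day 14, at the end of the time allowed before escalation. The hold is then at least 14 + 28 = 42 days, and 42/14 = 3 times the limit.

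All four rows fail. The gastrointestinal Grade 3 row also resumes after a taper, but M4112 is not visible in that cell, so it is not counted.

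**2. Resume rows against the Cycle 1 DLT rules**

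- *Hepatic Grade 2, in part.* The row covers ALT or AST above 3 and up to 5 x ULN, joined by and/or to a bilirubin band ("5 x ULN and/or total bilirubin > 1.5 to" 3 x ULN). The overlap with the 6.2.4 hepatic criterion is ALT or AST >3 to 5 x ULN with bilirubin 2 to 3 x ULN. For example, ALT 4 x with bilirubin 2.5 x ULN is in the row. If it is drug-attributed with no cholestasis or other cause, it is a DLT in Cycle 1 and an SMC re-exposure decision under 6.2.3. The row mentions neither. Values above 5 x (ALT or AST) or 3 x (bilirubin) fall in the Grade 3 to 4 row, which discontinues.
- *Endocrine Grade 3 or 4.* M4112 resumes on improvement. Section 6.2.4 exempts symptomatic thyroid dysfunction that resolves to Grade 2 within 6 days, but Grade 3 adrenal insufficiency is not among its exceptions.
- *Hypophysitis, severe or life-threatening.* M4112 resumes on improvement. By the scale in 7.4.1.1, severe is Grade 3 and life-threatening is Grade 4.
- *Suspected irAE, Grade 2 or 3.* Re-start may be considered once an irAE is ruled out, yet a Grade 3 nonhematological AE in Cycle 1 can be a DLT without being immune-related.
- *First Grade 3 irAE.* M4112 resumes after the taper.

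That makes at least five rows, and none visibly excludes Cycle 1.

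**3. The 6.2.3 hepatic bullet**

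The bullet above it is limited to events after the DLT assessment period. The hepatic bullet is not, so its re-exposure sentence can be read as reaching into Cycle 1, where 5.5.1 and 6.2.4 say stop.

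**The case against.** The strongest reply is that precedence is already clear. Table 9 is introduced as guidance that sites should follow, whereas the 2-week rule is a must and rules out exceptions by reason. Read that way, the limit wins and errs toward stopping. This reading is reasonable, but it turns the four resume instructions into dead text, and no visible sentence tells a site so.

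On DLTs, the reply is stronger. Section 5.5.1 requires withdrawal for Cycle 1 DLTs and separately for Grade 3 or higher AEs and irAEs as defined in 6.2.4. Section 6.2.4 repeats the DLT stop. Section 6.5.5, the parent of Table 9, requires discontinuation at Grade 3 or higher, apart from reactions mentioned in 6.2.3 and 6.2.4. A reader might infer that the protocol directs sites to re-treat after a DLT. It does not: a site would have to overlook all of these and, for liver events, the SMC sentence and the 24 h report to the Sponsor. What stands is that the rows do not carry the exclusion and no order of precedence is stated.

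Redaction also matters. Text before the 6.2.3 bullets and many drug cells in Table 9 are hidden, so an irAE exemption cannot be ruled out. A reader might infer that the full protocol contains none; the public copy cannot show that.

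A reader might also treat the 12-week limits at the end of Table 9 as a permitted M4112 delay that contradicts the 2-week rule. Those limits concern steroid need and persistence of an irAE, not a permitted hold of M4112, so the comparison is not made.

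**Conclusion.** Wrong as written on the visible text, and minor. Four Table 9 rows cannot be carried out under the 2-week limit: the taper alone is at least 14 days too long and at least twice the limit. At least five resume or re-start rows can include a Cycle 1 DLT without saying so. The hepatic Grade 2 row is the clearest gap because it omits both the DLT stop and the SMC decision.

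This rests on three assumptions. No redacted text exempts irAE tapers. Withholding continuously dosed M4112 counts as a treatment delay, as the gastrointestinal Grade 2 row's own use of the term for M4112 suggests. The 6.2.4 hepatic bullet is a DLT criterion in its own right, although the lead-in to that section speaks of Grade 3 or higher events.

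A reader might infer that DLT counts or the Bayesian dose recommendations are affected. They are not: DLTs are classified under 6.2.4 whatever Table 9 says about later treatment, and no statistical figure depends on these rows.

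**What to change.** - **Limit against taper.** Choose one: exempt irAE steroid tapers from the 2-week limit and state a maximum delay for them, or keep the limit and delete the M4112 resume text in the four rows.
- **Precedence.** Add one sentence, above Table 9 and in 6.2.3, that the Cycle 1 DLT stop in 5.5.1 and 6.2.4 overrides both.
- **Hepatic re-exposure.** Limit the SMC re-exposure sentence in 6.2.3 to events after the DLT period.
- **Hepatic Grade 2 row.** Exclude ALT or AST of at least 3 x ULN with bilirubin of at least 2 x ULN from the resume text, or make resumption there subject to the SMC.

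The cost is protocol wording only, with no change to sample size, visits or analysis. SAP Section 6 reports that the study was terminated early, before Parts IB and IC began, so the edit would mainly serve a later protocol that reuses these sections.
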